### 2.2 STUDY OBJECTIVES AND ENDPOINTS

#### 2.2.1 PRIMARY OBJECTIVE AND ENDPOINT

Objective	Endpoint	Start	End
To determine the efficacy of xisomab as measured by the incidence of CAT in individuals with a central venous catheter	Incidence of CAT	Catheter insertion (Day 1)	Day 18

## 2.2.2 SECONDARY OBJECTIVES AND ENDPOINTS

Objective	Endpoint	Start	End
To evaluate the safety and tolerability of xisomab 3G3 in cancer patients with a PICC or indwelling catheter	
 
1. Incidence of major and clinically-relevant bleeding [refer to Section 6.1.9.1]
 
2. Incidence of xisomab 3G3-associated toxicities [per CTCAE v5.0]
 
	Administration of xisomab 3G3 (Day 1 ± 2 days)	End of follow-up (Day 60)

## 2.2.3 EXPLORATORY OBJECTIVE AND ENDPOINT

Objective	Endpoint	Start	End
Assessment of drug exposure and catheter occlusions leading to medical intervention	
Quantification of coagulation profile:
 
 
1. aPTT
 
2. PK evaluation
 
3. Time to thrombosis (i.e., symptomatic CAT)
 
4. Proportion of participants with a catheter occlusion requiring medical intervention (i.e., local administration of tPA)
 
	pre-xisomab 3G3 administration	Day 18

### **3. STUDY ENROLLMENT AND WITHDRAWAL**

#### **3.1 PARTICIPANT INCLUSION CRITERIA**

To be eligible to participate in this study, an individual must meet all of the following criteria:

1. Participant or legally authorized representative (LAR) must provide written informed consent before any study-specific procedures or interventions are performed.
2. Men and women, aged  $\geq 18$  years.
3. In consultation with PI and treating physician, participant's cancer-directed therapy allows for a 1-day period between administration of study drug and subsequent start of planned cancer-directed therapy.
4. Individuals with a confirmed solid malignancy that will undergo insertion of a PICC line or indwelling central venous catheter as part of planned anticancer therapy per institutional standards
5. Must have ECOG performance status  $\leq 2$  (refer to Appendix A)
6. At time of enrollment, must have:
  - a. Platelet count  $> 100 \times 10^9/L$ ,
7. Female participants of childbearing potential must have a negative urine or serum pregnancy test within 72 hours prior to receiving the first dose of study medication. If the urine test is positive or cannot be confirmed as negative, a serum pregnancy test will be required.

Participants of childbearing potential are defined as any female who has experienced menarche and who has not undergone surgical sterilization (hysterectomy or bilateral oophorectomy) and is not postmenopausal.

8. Female participants of childbearing potential must agree to use adequate methods of contraception (Appendix B) starting with the first dose of study therapy through 90 days after the last dose of study therapy.

Participants of childbearing potential are those who have not been surgically sterilized or have not been free from menses for  $>1$  year without an alternative medical cause.

9. Male participants must agree to use an adequate method of contraception (Appendix B) starting with the first dose of study therapy through 90 days after the last dose of study therapy.

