Primary Objectives	To evaluate the antithrombotic efficacy of prophylactic xisomab 3G3 treatment in cancer patients with a central venous catheter.

Secondary Objectives	To determine the safety and tolerability of prophylactic xisomab 3G3 treatment as measured by the incidence and severity of adverse events in cancer patients with a central venous catheter.
Exploratory Objective	Assessment of participant coagulation profiles, and the incidence of line occlusion requiring medical interventions to obtain patency.
Primary Endpoints	The number of participants with catheter-associated thrombosis, as defined by the total incidence of symptomatic and asymptomatic thrombosis, and thrombotic occlusion leading to device failure (start: administration of xisomab; end: Day 18)
Secondary Endpoints	The number of subjects with treatment-related adverse events (TRAEs) and treatment-emergent adverse events (TEAEs) will be summarized using frequency counts (start: time of consent, end: Day 60)
Exploratory Endpoints	Quantification of coagulation parameters and assessment of catheter occlusion (start: pre-dose, end: Day 18 [i.e., post-dose]): 
 
a. Activated partial thromboplastin time (aPTT)
 
b. Pharmacokinetic (PK) evaluation
 
c. Time to symptomatic catheter-associated thrombosis
 
d. Proportion of participants with a catheter occlusion requiring medical intervention
 

Number of Participants	
Duration of Therapy	1 day
Duration of Follow Up	60 days [post catheter placement]
Key Inclusion Criteria	
 
• Men and women, aged <math>\geq</math> 18 years and members of all races and ethnic groups will be included.
 
• Participants with any solid tumor malignancy that will undergo insertion of a central venous catheter (PICC or indwelling subclavian vein central venous catheter) as part of planned cancer-directed therapy per institutional standards
 
• Able to wait 1 day post-study drug infusion before receiving cancer-directed therapy.
 
• ECOG performance status <math>\leq</math> 2
 
• Expected life expectancy of <math>>6</math> months
 
• At time of enrollment, must have adequate platelet count (<math>>100 \times 10^9/L</math>)
 

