A total of 50 participants are planned for enrollment into this study. Eligibility will be confirmed prior to planned PICC line placement or indwelling central venous catheter placement. Eligible participants that are scheduled to have a catheter inserted as part of their planned anticancer therapy will be enrolled to receive xisomab 3G3. Within 48 hours of insertion of the PICC or indwelling catheter (i.e.  $\pm$  2 days) per institutional standards, participants will undergo IV placement and receive a single dose of xisomab 3G3. Standard procedures for catheter maintenance for sterility and patency will be performed each time the catheter is accessed for use including 10 to 20 ml of normal saline pulsatile flush before and after use and every 7 days in the outpatient setting. Two days after administration of xisomab 3G3 participants may proceed with planned, standard-of-care anticancer treatment in consultation with their treating physician and in accordance with institutional guidelines. The **primary objective** is to measure the efficacy of xisomab 3G3, as determined by the incidence of ultrasound-confirmed CAT (both symptomatic and asymptomatic) within 18 days after catheter insertion, compared to historical cancer controls. All participants will undergo duplex venous ultrasound and physical examination to evaluate symptomatic or asymptomatic CAT at 14 ( $\pm$  4) days after catheter placement. If participants develop symptoms suggestive of CAT such as arm pain, swelling, or erythema in the arm with the PICC, those participants will undergo standard-of-care workup with a unilateral extremity duplex venous ultrasound in the affected arm or leg. Participants that have confirmed CAT or other thrombosis found on imaging, per investigator assessment, will be treated at the discretion of their treating physician per institutional guidelines and standards of care. The duplex venous ultrasound assessment will include evaluation of disease history and physical exam to further assess possible thrombosis-associated symptoms. The **secondary objective** is to establish the safety and tolerability of xisomab 3G3 administered near the time of central line placement in patients that are diagnosed with and treated for solid tumors. All participants will be followed for 60 days (or until resolution/stabilization of any clinically significant drug-related adverse event) from time of catheter insertion to assess for AEs and medication use.

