## 5. TREATMENT PLAN

### 5.1 DOSAGE AND ADMINISTRATION

Treatment will be administered on an *out-patient* basis. Reported adverse events and potential risks are described in Section 7.4, Adverse Event List.

Regimen Description			
Agent	Dose	Route**	Schedule
Xisomab 3G3	2 mg/kg	IV (via catheter)	Single dose administered within 48 hours of catheter placement ( $\pm$ 2 days).

\*\*Study drug should be administered as a slow bolus (approximately 1 minute).

Enrolled participants will receive a single fixed dose of xisomab 3G3 (2 mg/kg) through a peripheral IV or the inserted catheter within 48 hours of catheter placement (i.e.  $\pm$  2 days). If Xisomab 3G3 is administered prior to D1 catheter placement, eligibility must be confirmed prior to study drug administration. Participants will be monitored for at least 1 hour on the day of xisomab 3G3 administration for adverse events. Participants not receiving study drug or catheter placement as scheduled, may be rescheduled if within allowable screening window (i.e., no more than 28 days from consent). Participants receiving study drug but have a delay in placement of the catheter beyond 48 hours from time of xisomab administration, will not be considered evaluable for efficacy analysis (per Section 8.1), but will be followed for xisomab 3G3-associated toxicities (per Section 6.7).

Two (2) days after participants receive study drug they may proceed to undergo planned anticancer therapy per standard of care. Administration of planned cancer-directed therapy may not occur earlier than 2 days from time of giving study drug. The type(s) and frequency of administration of anticancer drug(s) comprising the participants' anticancer treatment regimen is at the discretion of treating physician and should be recorded in the CRF.

Consistent with institutional standards, participants may at any time during the study receive a standard of care workup with an ultrasound if they develop symptoms the investigator (or treating physician) believes to be suggestive of CAT, including arm pain and swelling or erythema in the same arm as the catheter. In such cases, the participant may receive antithrombotic therapy, at the discretion of their treating physician, per institutional guidelines.

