### 8.1 ANALYSIS POPULATIONS

An intent to treat (ITT) analysis set consists of all participants who consent and enroll in the trial regardless of whether they are exposed to the study drug. An efficacy analysis set consists of participants who have placement of a catheter, receive xisomab 3G3 within 48 hours of catheter placement, and have at least one CAT assessment (i.e., ultrasound and physical exam) by Day 18 of the study. A safety analysis set consists of all participants who are exposed to the single dose of study drug.

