### 8.2 DESCRIPTION OF STATISTICAL METHODS

#### 8.2.1 GENERAL APPROACH

This is a single arm phase II trial to assess the efficacy of xisomab 3G3 in reducing the incidence of CAT over 18 days after catheter placement. This study will enroll 50 patients with non-leukemic cancer who are to undergo placement of a central venous catheter and who can wait 2 days from xisomab infusion before initiating antineoplastic therapy.

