### 8.3 SAMPLE SIZE, POWER, ACCRUAL RATE AND STUDY DURATION

#### 8.3.1 SAMPLE SIZE AND POWER

Based on the central venous catheter thrombosis rates and other parameters (e.g., population type, thrombosis evaluation period) in prior studies, the sample size calculation makes the assumption of a 60% incidence of ultrasound-confirmed CAT (i.e., both symptomatic and asymptomatic) over 18 days post- catheter placement in cancer patients not treated with xisomab. A sample size of 50 participants, accounting for a 4% efficacy ineligibility rate, is sufficient to provide 80% power to detect a 20 percentage point reduction in the incidence of CAT at a two-sided  $\alpha$  of 0.05.

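### Eligibility asks only that cancer therapy can wait 1 day after study drug, but section 5.1 bars it earlier than 2 days

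*Combined protocol and SAP*

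**What the plan says.** Five places in the combined protocol and SAP state how long cancer-directed therapy must or can wait after study drug.

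Two are eligibility statements, and both use 1 day:
- Section 3.1, item 3: the regimen, judged together with the PI and the treating physician, "allows for a 1-day period between administration of study drug and subsequent start of planned cancer-directed therapy".
- Synopsis, key inclusion criteria: "Able to wait 1 day post-study drug infusion before receiving cancer-directed therapy".

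Three are in other sections, and all use 2 days:
- Section 2.1: "Two days after administration of xisomab 3G3 participants may proceed with planned, standard-of-care anticancer treatment".
- Section 5.1: "Administration of planned cancer-directed therapy may not occur earlier than 2 days from time of giving study drug".
- Section 8.2.1, describing the 50 patients to be enrolled: "who can wait 2 days from xisomab infusion before initiating antineoplastic therapy".

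**The concern.** An eligibility criterion of this kind is there to select patients who can follow the treatment plan. Here the screening minimum is shorter than the treatment minimum, so the criteria let through the very patients who cannot meet the rule that applies after dosing.

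For a patient whose therapy can wait 1 day but not 2, two outcomes are possible. Therapy starts inside the period that 5.1 closes, which is a protocol deviation. Or therapy is held to satisfy 5.1, which is longer than the wait that was assessed when eligibility was confirmed. The Synopsis and section 1.4.2 count delays in cancer treatment among the harms of catheter thrombosis that the trial hopes to reduce, so a longer hold is not a neutral outcome. Such a patient would also fall outside the enrolled population that 8.2.1 describes.

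**Working it through.** **1. The five statements side by side**

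| Place | Gap | Counted from | Force |
|---|---|---|---|
| Synopsis, key inclusion criteria | 1 day | study drug infusion | eligibility |
| 3.1, item 3 | 1 day | study drug administration | eligibility |
| 2.1 | 2 days | study drug administration | permissive |
| 5.1 | at least 2 days | time of giving study drug | prohibition |
| 8.2.1 | 2 days | infusion | description of those enrolled |

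**2. Who falls between the rules.** Let *w* be the longest time, in days after dosing, that a patient's cancer therapy can wait. The eligibility text requires *w* ≥ 1. Compliance with 5.1 requires *w* ≥ 2. Patients with 1 ≤ *w* < 2 pass the first test and fail the second. The width of that band is 2 − 1 = 1 day, or 24 hours. The documents do not say how *w* is distributed, so the number of patients in the band cannot be estimated.

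**3. Can the two figures be read as the same interval?** Item 3 of section 3.1 could mean one clear day between dosing and therapy, with therapy on the second calendar day. That would fit 2.1 and 5.1. It does not fit the rest of the text. The Synopsis and 8.2.1 both describe a wait that starts at the infusion, and one gives 1 day where the other gives 2. The calendar-day reading would only move the conflict, because the Synopsis would then disagree with 3.1 as well.

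**4. Does the gap enter the statistics?** The plan's own sample size was reproduced first. Section 8.3.1 supplies "60% incidence of ultrasound-confirmed CAT" in untreated patients and a "20 percentage point reduction in the incidence of CAT", so p0 = 0.60 and p1 = 0.40, with two-sided alpha 0.05, 80% power and 4% ineligible for efficacy. Using the normal approximation for one proportion:

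n = (z₀.₉₇₅·√(p0(1−p0)) + z₀.₈₀·√(p1(1−p1)))² / (p0−p1)²

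Both variance terms are 0.24, so n = (1.960 + 0.842)² × 0.24 / 0.04 = 47.09, or 48 evaluable. Then 48 / 0.96 = 50, which matches the plan. The waiting interval is not an input.

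The efficacy set in section 8.1 requires that participants have a catheter placed, "receive xisomab 3G3 within 48 hours of catheter placement, and have at least one CAT assessment" by Day 18. It sets no condition on when cancer therapy starts. Neither do the intent-to-treat and safety sets. The primary analysis in 8.2.2 uses the efficacy set, so a patient in the band would be counted like any other.

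**The case against.** The strongest reply is that only one of the three 2-day statements binds anyone. Section 2.1 is permissive, 8.2.1 is descriptive, and the prohibition is in 5.1 alone. That stands. A reader might infer that the design, treatment and statistics sections all impose a 2-day minimum, and they do not. One binding rule is still enough to conflict with the eligibility text.

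A second reply points to existing safeguards. The PI takes part in the judgement under item 3. Exclusion 6 lets the investigator turn away someone whose circumstances would limit compliance. Dosing may come up to 2 days before catheter placement, which leaves room for scheduling. These may well keep the number affected low. They are discretionary, however, and item 3 directs the consultation to a 1-day wait. The fair statement is that the criteria do not exclude such patients, not that such patients will be enrolled.

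Three further inferences are tempting, and the documents do not support them:

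- **That the analysed population is compromised.** Section 8.2.1 describes who is enrolled. The analysis sets are defined in 8.1, and none refers to the gap.
- **That early drug reactions would be confounded by chemotherapy.** Causality is judged partly on timing (7.2.5), and known adverse events of the cancer regimen are largely not collected (6.1.9, 7.5), so the thought is natural. But the protocol gives no rationale for the gap. Follow-up runs to Day 60, and section 1.3 reports an aPTT effect still present at day 14. Overlap with cancer therapy is therefore built in under either interval, and nothing shows what 24 hours would change.
- **That the treating physician has not agreed to the longer wait.** That physician is consulted under both 2.1 and 3.1. What can be said is only that item 3 tests 1 day while 5.1 imposes 2.

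**Conclusion.** Wrong as written, and minor. The eligibility test in the Synopsis and section 3.1 is looser than the mandatory rule in 5.1 by 24 hours, and no section resolves it. The consequence is limited to possible deviations from 5.1, or cancer therapy held longer than was assessed at screening, in patients who can wait 1 day but not 2. How many there are is unknown and could be zero. The sample size of 50, the three analysis sets and the primary analysis are unaffected.

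The conclusion assumes that the Synopsis and 8.2.1 mean what they say in counting the wait from the infusion. It takes no view on which interval was intended, because the documents do not settle that.

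**What to change.** Reconcile the Synopsis and sections 2.1, 3.1 (item 3), 5.1 and 8.2.1 to a single interval, so that the eligibility test equals the treatment rule. Count it everywhere from the time of study drug administration, which also removes the calendar-day ambiguity in item 3. The sponsor should decide which interval is right on clinical grounds; none is proposed here.

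Depending on that decision, the figure changes either in the two eligibility statements or in the three other sections. The cost is amendment wording, with the committee and IRB approval that section 11.5 requires. It needs no extra data, no extra patients and no change to the analysis.

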#### **3.2 PARTICIPANT EXCLUSION CRITERIA**

An individual who meets any of the following criteria will be excluded from participation in this study:

1. Actively receiving treatment in another therapeutic clinical trial
2. Active acute leukemia (lymphoma and myeloma are allowed)
3. At time of enrollment, known contraindication to anticoagulation therapy, including:
  - a. Clinically significant active bleeding

- b. Individual is within 72 hours of major surgery
- c. Abnormal baseline coagulation tests, including INR > 1.5, or aPTT prolonged
- d. Abnormal renal function defined by an eGFR < 45 mL/min
- e. Abnormal hepatic function defined as LFTs (AST, ALT or Total Bilirubin) >2x the upper limit of normal or known Child-Pugh class B or C cirrhosis.
- f. Prior history of intracranial hemorrhage
- g. Primary brain tumors or known brain metastasis
- h. Major extracranial bleed within the last 6 months where the cause has not been identified or treated
- i. Known bleeding diathesis
- j. Use of therapeutic anticoagulation or anti-platelet agents for any indication at enrollment
- k. At the discretion of the investigator, any other contraindication to anticoagulation therapy
- l. Presence of a pediatric-sized PICC line
- m. Participant is expected to receive chemotherapy associated with a 15% or higher incidence of grade 3-4 thrombocytopenia within 14 days of receiving study drug.

4. Preexisting intravenous catheter, or indwelling spinal or epidural catheter, at time of enrollment that is intended to remain for the duration of study. Participants may remain eligible if existing catheter is to be removed before placement of a catheter for cancer directed therapy. Removal of existing catheter should occur at least 24 hours prior to PICC or indwelling catheter insertion.

5. Previously documented hypersensitivity to either the drug or excipients

6. Psychiatric illness/social situations, or any other condition, that in the opinion of the investigator, would limit compliance with study requirements

7. Participant is pregnant or breastfeeding, or expecting to conceive or father children within the projected duration of the trial, starting with the screening visit through 90 days after the last dose of trial treatment.

8. Participant is allergic to heparin or heparin derivatives.

9. Participants with a history of venous thromboembolism within the last 3 months.

### 3.3 STRATEGIES FOR RECRUITMENT AND RETENTION

Participants for this study will primarily be recruited from hematology and oncology practices within OHSU, including affiliated community hematology and oncology (CHO) practices.

Participants may be identified and referred to this study by their primary treating physician from within OHSU/CHO, or from the outside community. Participants may be identified by a member of the patient's treatment team, the PI, research team, or medical and surgical oncology clinics part of OHSU/CHO. As a member of the treatment team, the investigator will screen their patient's medical records for suitable research study participants and discuss the study and their potential for enrolling in the research study. Referral of potential participants to investigator of this study is made as part of standard of care, with the referring physician seeking advice on the diagnosis, evaluation, and/or treatment of the patient's malignancy.

The investigators may also screen the medical records of potential participants with whom the investigator does not have a treatment relationship. This will be done for the limited purpose of identifying patients who would be eligible to enroll in the study and to record appropriate contact information in order to approach these potential individuals regarding the possibility of participating in the study. Participants may also initiate contact with the investigator through information of this study posted on the [clinicaltrials.gov](https://clinicaltrials.gov) website.

### 3.3.1 ACCRUAL ESTIMATES

No OHSU Knight Cancer Institute study will focus on any particular gender, racial or ethnic subset. No participant will be excluded from the study on the basis of sex, gender, racial or ethnic origin. Male, female and minority volunteers will be recruited for this study from the general population and approximately 50% men and 50% women will be studied. Gender-nonconforming and gender-fluid individuals as members of the general population will also be recruited. The projected sex, gender, racial, and ethnic composition of the study will represent that of the state of Oregon (**Table 1**).

Table 1. Oregon Population Demographics and Projected Accrual						
Ethnic Category [OR]	Sex/Gender					
	Females		Males		Total	
	n	%	n	%	n	%
Hispanic or Latino	3	6.5	3	6.3	6	12.8
Not Hispanic or Latino	22	44.0	22	43.2	44	87.2
Ethnic Category: Total of all participants*	25		25		50	100*
Racial Category						
American Indian or Alaskan Native	0	0.9	0	0.9	1	1.8
Asian	1	2.3	1	2.2	2	4.5
Black or African American	1	1.1	1	1.0	1	2.1
Native Hawaiian or other Pacific Islander	0	0.2	0	0.2	0	0.4
White	22	44.1	22	43.3	44	87.4
Two or more races	1	1.9	1	1.9	2	3.8
Racial Category: Total of all participants*	25	50.5	25	49.5	50	100
Source: Adapted from U.S. Census Bureau, 2017.						
*Totals may not equal 100 due to rounding.						

